3.7.4.1. Abemaciclib

For participants in Arm A, abemaciclib will be administered at a starting dose of 55 mg/m² PO BID continuously throughout the study unless interrupted for toxicity. Doses will be administered at approximately the same times on each day. Please see [Attachment 6](#) (abemaciclib dosing chart) to determine if a change in BSA necessitates a change in abemaciclib dosing.

Abemaciclib is provided as either 25 mg tablets, 50 mg tablets, or 2.5 mg granules. CCI

Abemaciclib should be taken BID (with at least approximately 6 hours separating doses) at the same time each day.

Participants taking abemaciclib tablets should be instructed to swallow tablets whole and not chew or crush them. If the participant is unable to swallow the abemaciclib tablets or oral granules, please refer to Section 3.7.7. Participants taking oral granules should follow the provided instructions for using the measuring device and administering the drug.

CCI

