3.6. Study Population

3.6.1. Inclusion Criteria

Participants are eligible to be included in the Study JP04 only if they meet all of the inclusion criteria in Section 6.1 of the **CAMPFIRE Master Protocol** and the following criteria:

Age and Weight

[35] Participants aged 1 to <40 years

[36] Body weight ≥ 10 kg

Disease and Participant Characteristics

[37] Eligibility will be based on a diagnosis of Ewing's sarcoma or Ewing's sarcoma-like tumor by institutional pathologist at time of original diagnosis. The original pathological report is required. Repeat biopsy at progression is not required

[38] Must be able to swallow and/or have a gastric/nasogastric tube

a) Participants in the European Union must be able to swallow intact capsules

[39] If on systemic steroids at study entry, the dose must be stable or decreasing during the 7 days prior to C1D1

[40] Life expectancy of at least 8 weeks and able to complete at least 1 cycle of treatment

[41] Participants/caregivers are able and willing to make themselves available for the duration of the study and are willing to follow study procedures, including adherence to the PK sampling schedule

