3.7. Treatments

3.7.1. Treatments Administered

Table JP04.6 shows the treatment regimens.

Table JP04.6. Treatment Regimens

Starting Doses Cycle = 21 days				
	Abemaciclib PO		Irinotecan IV (Days 1-5 each cycle)	Temozolomide PO (Days 1-5 each cycle)
	<18 years	≥18 years		
Arm A	55 mg/m ² BID (max dose 100 mg BID)	100 mg BID	50 mg/m ² /day × 5	100 mg/m ² /day × 5
Arm B	None		50 mg/m ² /day × 5	100 mg/m ² /day × 5
Authorized as defined by EU Clinical Trial Regulation	Authorized and not used according to EU authorization		Authorized and not used according to EU authorization	Authorized and not used according to EU authorization

Abbreviations: BID = twice daily; IV = intravenous; PO = orally.

Participants will begin dosing-assigned treatment on Cycle 1 Day 1. A cycle is defined as an interval of 21 days timed to irinotecan and temozolomide. The 21-day cycle, anchored to irinotecan and temozolomide, should be maintained throughout the treatment phase. Cycles may not be less than 21 days.

When delays are required, doses should be resumed at the earliest medically appropriate opportunity based on investigator judgment and dose adjustment guidelines (Section 3.7.8).

Treatment will continue until progression, unacceptable toxicity, or other discontinuation criteria are met (Section 3.8).

A delay to the start of a cycle of a dose due to holiday, weekend, weather, or other unforeseen circumstances will be permitted for a maximum of 7 days and not counted as a protocol deviation. In exceptional circumstances, a delay of >7 days is permitted upon agreement between the investigator and the Lilly CRP/CRS. Abemaciclib treatment may continue during the delay if there is sufficient drug supply and if there are no toxicities that would prevent treatment.

Irinotecan and temozolomide must be administered on 5 consecutive days.

Packaging and labeling

Treatments administered in the study will be supplied by the sponsor in accordance with current Good Manufacturing Practice. Study interventions will be labeled as appropriate for country requirements.

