3.7.4. General Dosing Instructions

Obesity: For participants with a BMI ≥ 30 kg/m², the American Society of Clinical Oncology Guidelines recommends calculation of dose using the actual body weight for calculation of body surface area- or weight-based dosing (ASCO [Griggs et al. 2012]).

For each cycle, the actual dose administered for study drugs must be within 10% of the planned dose; any total cycle dose that is not within 10% (either $> 110\%$ or $< 90\%$) of the planned dose will result in a protocol deviation. Please contact the Lilly CRP/CRS to discuss any questions for individual situations.

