Attachment 6. Protocol JP04 Addendum Abemaciclib Dosing Chart

BSA (m ²) for participants <18 years ^a	Abemaciclib dose (mg)
0.2	CCI
0.21-0.24	CCI
0.25-0.29	CCI
0.3-0.34	CCI
0.35-0.38	CCI
0.39-0.43	CCI
0.44-0.68	CCI
0.69-1.13	CCI
1.14-1.59	CCI
1.60+	CCI
All participants ≥18 years	CCI

^a BSA calculations are made using the Mosteller formula (Mosteller 1987)

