7.9.1. Extent of Exposure

Drug exposure, dose intensity, and drug adjustments (dose omissions and reductions) will be summarized for abemaciclib, for temozolomide, and for irinotecan. Drug exposure will include summaries of cycles received per patient, duration on therapy, and cumulative dose. Dose intensity will be calculated as the actual cumulative amount of drug taken divided by the duration of treatment. Relative dose intensity will be calculated as

$$\frac{\text{the amount of actual drug taken}}{(\text{the amount of drug prescribed})} \times 100\%$$

(expressed as a percentage). The summary of dose adjustments and omissions will include the reason for adjustment or omission.

Extent of exposure for abemaciclib will be measured by pill counts for tablets and capsules, and by weights for oral granules. Dose intensity will be expressed in mg/day. The assigned cumulative dose while on study is 2 doses per day \times planned amount of drug dose (dependent on dose level and patient BSA at the beginning of each cycle) \times number of days on treatment.

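### Protocol 3.7.4.1 conflicts with Table JP04.6, the synopsis and Attachment 6 on the adult abemaciclib starting dose; the SAP 7.9.1 planned-dose wording should follow the reconciled rule

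*Protocol*

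**What the plan says.** **Protocol 3.7.4.1** opens with "For participants in Arm A, abemaciclib will be administered at a starting dose of 55 mg/m² PO BID continuously throughout the study", subject to interruption for toxicity. The sentence has no age limit and no cap. The section then points to Attachment 6 for deciding whether a change in BSA changes the dose.

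**Protocol 3.7.1, Table JP04.6**, and the matching table in the synopsis (3.1) have two abemaciclib columns. Below 18 years the entry is 55 mg/m² BID with the limit "max dose 100 mg BID"; from 18 years it is 100 mg BID.

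**Attachment 6** labels its BSA rows "for participants <18 years" and adds one row for "All participants ≥18 years". The doses in the chart are redacted.

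**Protocol 3.6.1** admits "Participants aged 1 to <40 years", and 3.7.2 stratifies randomization at 18 years, so adults are a planned part of Arm A.

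**Protocol 3.7.4** requires that "the actual dose administered for study drugs must be within 10% of the planned dose", and makes a total cycle dose outside that range a protocol deviation.

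**SAP 7.9.1** builds the assigned cumulative abemaciclib dose from a "planned amount of drug dose (dependent on dose level and patient BSA at the beginning of each cycle"), two doses a day, and days on treatment. It separately defines relative dose intensity (RDI) as drug taken divided by "the amount of drug prescribed".

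**The concern.** A site dosing an Arm A adult from 3.7.4.1 alone would calculate from BSA. A site using Table JP04.6 or the synopsis would give the flat entry. An instruction for an enrolled age stratum should not depend on which page is opened. The ±10% rule inherits the problem, because the same administered dose can be compliant under one reading and a deviation under the other.

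The SAP carries the ambiguity into the exposure tables. Its planned-dose term depends on BSA and makes no distinction for adults. It does not say whether the dose level is the starting or the current one, and it does not link this term to the RDI denominator. The abemaciclib exposure summary for adults could then be programmed in more than one way.

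**Working it through.** The documents state no RDI value, so there is no plan figure to reproduce. The check sets the passages side by side and sizes the gap.

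**Inputs from the documents:** 55 mg/m² BID (3.7.4.1; also the under-18 column of Table JP04.6); 100 mg BID from 18 years (Table JP04.6, synopsis); 100 mg cap in the under-18 column; ±10% limit (3.7.4).

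**Assumptions not in the documents:** adult BSA of 1.4 to 2.3 m²; for the RDI illustration, a reduced dose of 75 or 50 mg BID, since the reduction levels are not in the available text.

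| Place | Below 18 years | 18 years and over |
|---|---|---|
| 3.7.4.1 | 55 mg/m², no cap in the sentence | same sentence, no age limit |
| Table JP04.6, synopsis | 55 mg/m², max 100 mg | 100 mg |
| Attachment 6 | BSA rows | one row, no BSA |

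**Step 1: size of the gap (mg per dose).** Dose = 55 × BSA.
- BSA 1.4: 55 × 1.4 = 77 mg, 23% below 100 mg.
- BSA 2.3: 55 × 2.3 = 126.5 mg, 26.5% above 100 mg.
- Equality: 100 / 55 = 1.82 m².

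**Step 2: the ±10% rule.** With the same number of doses in a cycle, the per-dose ratio carries over to the cycle total.
- Plan read as uncapped 55 × BSA, 100 mg given: within limits from 100 / (1.1 × 55) = 1.65 to 100 / (0.9 × 55) = 2.02 m².
- Plan read as 100 mg, 55 × BSA given: within limits from 90 / 55 = 1.64 to 110 / 55 = 2.00 m².
- If the 100 mg cap were also applied to adults, the gap above 1.82 m² would vanish and only the lower limit would matter.

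**Step 3: the RDI denominator.** Take an adult who starts at 100 mg BID (the table entry, for illustration only), is reduced for half the treatment time, and takes every dose.
- Against the starting dose: (0.5 × 100 + 0.5 × 75) / 100 = 87.5%, or (0.5 × 100 + 0.5 × 50) / 100 = 75%.
- Against the currently prescribed dose: 100% in both cases.
- Dose intensity in mg/day falls either way, from 2 × 100 = 200 to 2 × 87.5 = 175 or 2 × 75 = 150.

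**The case against.** Four arguments weigh against the point.

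**Redaction.** Parts of 3.7.4.1 are blacked out, as is the text in 3.5.5 directly after the statement that the study includes adults and children. An adult rule may stand there. This limits the claim to the visible text. The opening sentence of 3.7.4.1 is itself unredacted and still reads as applying to all of Arm A.

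**The chart governs.** 3.7.4.1 refers to Attachment 6, which doses by bands and treats adults separately. One dose can stay within ±10% of 55 × BSA only across a band whose upper-to-lower ratio is at most 1.1 / 0.9 = 1.22. The 0.69–1.13 band has ratio 1.64 and the 1.14–1.59 band 1.39. Even for minors, then, the workable planned dose is the chart dose, not raw 55 × BSA. This stands, and it makes the uncapped figures an upper illustration of the gap, not a forecast. The protocol nevertheless does not say that the chart overrides the sentence.

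**Adult RDI is not shown to be wrong.** A reader might infer that the SAP divides adult doses by 55 × BSA, giving an adherent adult on 100 mg an RDI of 100 / 82.5 = 121% at BSA 1.5 or 100 / 121 = 83% at BSA 2.2. The documents do not support that. RDI divides by the amount prescribed, which the SAP never equates with the BSA-based assigned dose. An adult prescribed 100 mg who takes 100 mg has RDI 100% under the formula as written.

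**Reductions do not disappear.** A reader might also infer that the exposure tables hide dose reductions, or cannot show reduced irinotecan and temozolomide delivery. SAP 7.9.1 summarizes cycles, cumulative dose, dose intensity, omissions and reductions with reasons for all three drugs. SAP 7.4 adds dose delays, and 7.9 reports by arm. The SAP refers to the dose level without saying that it is a reduced one. Measuring RDI against the starting or the prescribed dose is a matter of convention; what is missing is a statement of which applies.

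**Conclusion.** The point holds as a conflict between visible dosing passages for adults. 3.7.4.1 gives one BSA-based starting dose for Arm A, while Table JP04.6, the synopsis and the layout of Attachment 6 treat adults separately. That rests on the wording alone. Its size rests on the assumed adult BSA and on an uncapped reading: −23% to +26.5% across 1.4 to 2.3 m², with agreement only near 1.82 m². Outside roughly 1.65 to 2.0 m² the choice of rule decides whether a dose meets the ±10% limit.

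The reconciliation is needed because it concerns an instruction to sites and a deviation rule. The SAP part is a clarification of a descriptive summary. It feeds neither the primary PFS analysis nor the futility rule, and it does not establish that any reported RDI would be wrong. Hidden text could narrow the dosing conflict, but the sentence in 3.7.4.1 would still need to agree with it.

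**What to change.** 1. Reconcile the opening sentence of Protocol 3.7.4.1 with Table JP04.6, the synopsis and Attachment 6, so that one adult starting-dose instruction is stated. Which one is a decision for the sponsor. The ±10% check in 3.7.4 then has a single reference dose.
2. Align the assigned cumulative dose in SAP 7.9.1 with the reconciled rule, for adults and minors.
3. At lower priority, state in SAP 7.9.1, for each drug, whether the RDI denominator is the participant's assigned starting dose or the currently prescribed dose. The SAP spells out an assigned dose only for abemaciclib. If the prescribed dose is kept, note that reductions will not lower RDI and must be read from dose intensity, cumulative dose and the reduction summaries.

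The cost is wording in one protocol section and one SAP section. No new data collection is needed, and the primary analysis does not change. If the starting dose is chosen as denominator, reported RDI will be lower for participants whose dose was reduced.

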3.7.4.2. Irinotecan

Irinotecan will be administered at a starting dose of 50 mg/m²/day as an IV infusion over 90 minutes (unless approved otherwise by the Lilly CRP/CRS) on Days 1-5 of each cycle unless interrupted for toxicity. It is recommended to allow a minimum of 20 hours between sequential days of irinotecan dosing.

Participants with prior abdominal/pelvic radiotherapy, or total body irradiation for bone marrow transplantation should have irinotecan dose reduced to 37.5 mg/m²/day at start of therapy.

Impaired glucuronidation: Participants known to have reduced UGT1A1 activity, such as an UGT1A1*28 or UGT1A1*6 allele, may have increased risk of hematological toxicity and/or

diarrhea. An irinotecan dose reduction at the start of therapy should be considered for these participants. Additionally, participants with reduced UGT1A1 activity should be carefully monitored for hematologic toxicities and diarrhea. UGT1A1 testing is not required.

3.7.4.3. Temozolomide

Temozolomide will be administered at a starting dose of 100 mg/m²/day PO daily on Days 1-5 of each cycle unless interrupted for toxicity. Except for C2D1 and C4D1 when PK collection is required and temozolomide must be administered at the study site, temozolomide may be administered either at home or on-site. Doses may be rounded per local clinical practice. Temozolomide should be administered on an empty stomach approximately 1 hour prior to irinotecan infusion and can be administered with abemaciclib. If a participant spits out or vomits temozolomide within 15 minutes of ingestion, the dose should be repeated. If vomiting occurs a second time, the dose should not be repeated. IV temozolomide is not allowed.

3.7.4.4. Supportive Care

Participants should receive full supportive care to maximize quality of life. All supportive care should be recorded on the eCRF.

- The use of G-CSF is permitted for all cycles, including first cycle, based on ASCO (Smith et al. 2015) and European Society for Medical Oncology (Crawford et al. 2010) guidelines. Administration of G-CSF is encouraged for all participants, regardless of treatment arm, at high risk of neutropenia based on investigator's judgment.
- If clinically indicated, erythropoietin, packed red blood cell transfusions, and other blood products may be used according to the ASCO guidelines (Rizzo et al. 2008).
- Prophylactic antibiotic treatment should be consistent with ASCO guidelines (Lehrnbecher et al. 2017).

3.7.4.5. Premedication

Nausea and vomiting have been frequently reported with irinotecan and temozolomide. Prophylactic anti-emetics(s) are recommended before each daily treatment with irinotecan and temozolomide.

Consider atropine IV or subcutaneous in participants with cholinergic symptoms (e.g., increased salivation, rhinitis, miosis, diaphoresis, and abdominal cramping) or early-onset diarrhea-associated with irinotecan.

3.7.4.6. Supportive Management for Diarrhea

Both abemaciclib and irinotecan frequently cause diarrhea. Importantly, participants should receive instructions on the management of diarrhea at the start of each cycle. Along with standard fluid and electrolyte management, loperamide is recommended. Though it may be difficult, investigators should determine the most likely cause of diarrhea as therapeutic interventions differ according to the offending agent.

3.7.4.6.1. *Diarrhea suspected due to irinotecan*

Early diarrhea occurs during or shortly after irinotecan infusion. It is usually transient and infrequently severe. It may be accompanied by cholinergic symptoms of rhinitis, increased salivation, miosis, lacrimation, diaphoresis, flushing, and abdominal cramping.

Prophylactic or concomitant use of antibiotics, such as cefixime and cephalosporin, can be used for irinotecan-associated diarrhea at the investigator's discretion (Wagner et al. 2008). Refer to prescribing information for additional management of diarrhea attributed to irinotecan.

Early diarrhea and the associated cholinergic symptoms may be prevented. Consider prophylactic or therapeutic administration of atropine (according to label or institutional practice) unless clinically contraindicated.

Late diarrhea occurs ≥ 24 hours after irinotecan infusion, can be prolonged, and may lead to dehydration, electrolyte imbalance, or sepsis. Late irinotecan-induced diarrhea can be complicated by colitis, ulceration, bleeding, ileus, obstruction, infection. It can be life-threatening.

3.7.4.6.2. Diarrhea suspected due to abemaciclib

Diarrhea was the most frequently reported TEAE with abemaciclib in the adult Phase 3 registration studies (MONARCH 2 [Sledge et al. 2017]; MONARCH 3 [Goetz et al. 2017; Johnston et al. 2019]; monarchE [Johnston et al. 2020]). Diarrhea was generally manageable with standard anti-diarrheal agents and dose adjustment.

3.7.4.6.3. Management of Diarrhea

It is important for all participants to receive education about diarrhea potential with irinotecan and abemaciclib before beginning therapy. Diarrhea related to abemaciclib is most frequent in the early cycles and is manageable with supportive measures. These should be discussed before symptoms arise so that participant and caregivers are prepared.

“Participants should be instructed regarding the use of anti-diarrhea therapy (e.g., loperamide or local standard of care)”. Participants should be encouraged to drink at least maintenance volumes of fluids based on their age and body size.

Participants and caregivers should be in communication with the investigative site for recommendations to monitor and replace fluid and electrolytes. Site personnel should assess participant by phone or at the site within 24 hours of diarrhea onset to monitor hydration status and diarrhea severity.

If associated with severe nausea and/or vomiting such that the participant is unable to maintain hydration with enteral fluids, then the participant should be admitted for IV hydration, electrolyte replacement, and close monitoring.

If diarrhea is associated with fever or severe neutropenia, broad-spectrum antibiotics should be prescribed per institutional guidelines.

Follow dose-modification guidance in Section 3.7.8.3.2, including dose suspension and/or reduction as appropriate.

3.7.5. *Pneumocystis* prophylaxis

Pneumocystis jirovecii pneumonia may occur in participants receiving irinotecan and temozolomide. This risk is increased in those receiving corticosteroids or with longer treatment regimens. PCP prophylaxis is encouraged.

3.7.6. Concomitant Therapy

No other chemotherapy, investigational medications, immunotherapy, hormonal cancer therapy, herbal supplements and/or herbal drugs intended to treat cancer will be permitted while participants are on study treatment.

Palliative radiation and surgery for cancer may be allowed after discussion with the Lilly CRP.

A list of restricted and excluded concomitant therapies and exceptions is provided in [Attachment 5](#). All premedication, supportive care, and concomitant medication must be reported on the CRF at each visit.

3.7.7. Participants with Difficulty Swallowing

If, after initiating study treatment, a participant develops difficulty swallowing, the following should be considered.

Abemaciclib:

- CCI [REDACTED]
- [REDACTED]
- [REDACTED]
- [REDACTED]
- [REDACTED]
- [REDACTED]
- [REDACTED]

Temozolomide:

- follow standard of care for alternative administration (Trissel et al. 2006; CCLG 2016).
- IV administration of temozolomide is not allowed.
- CCI [REDACTED]

3.7.8. Dose Modification

3.7.8.1. Planned or anticipated logistical delays

For planned logistical delays (including but not limited to vacation or holidays), additional abemaciclib may be dispensed and continued until next scheduled site visit. In the event that the participant has met criteria to begin the next cycle, but the start (i.e., Day 1) is delayed due to logistical reasons, so long as the participant has adequate abemaciclib supply, they should continue until next Day 1 visit. If a treatment is interrupted due to inadequate abemaciclib supply, the cycle will continue and next irinotecan and temozolomide administrations should remain on previous schedule; in other words, the missed abemaciclib doses will not be made up.

For participants undergoing surgery, refer to the following guidelines for abemaciclib dose modifications:

- Minor surgeries and procedures: investigators should treat as clinically indicated and closely monitor any signs of infection or healing complications.
- Major surgeries: suspend abemaciclib for ≥ 7 days before surgery and resume as clinically indicated.
- Both absolute neutrophil and platelet counts should be adequate before resuming abemaciclib. Surgical wounds should be without infection and healing well.
- Dose suspensions ≥ 21 days must be discussed with Lilly CRP/CRS.

3.7.8.1.1. Additional Guidance for Surgeries

If a tumor becomes operable while on study treatment, the participant may undergo surgical resection to remove the lesion. A participant who undergoes surgery is not considered noncompliant and does not incur a protocol deviation.

3.7.8.2. Discontinuation of One Study Treatment

Participants may discontinue irinotecan and/or temozolomide (due to chemotherapy-associated toxicities) while continuing abemaciclib upon discussion with the Lilly CRP/CRS. If abemaciclib must be discontinued, participants may continue to receive irinotecan and/or temozolomide. For all study drugs, if dose reductions are required beyond the lowest dose, the drug should be discontinued. Continuation on chemotherapy beyond Cycle 12 will be up to the investigator's discretion and the individual participant's situation. Prior to continuing the participant on chemotherapy beyond Cycle 12, the investigator should discuss with the Lilly CRP/CRS. Abemaciclib may continue beyond Cycle 12 until discontinuation criteria is met.

Dose Modification for Neutropenia						
Note: For hematologic toxicities, dose holds, and reductions - apply simultaneously to all drugs as indicated						
	Abemaciclib		Irinotecan		Temozolomide	
Severity and Duration	Dose Hold	Dose Reduction	Dose Hold	Dose Reduction	Dose Hold	Dose Reduction
Grade 3	Recommend G-CSF in subsequent cycle					
Grade 4 Initial incident	Hold until ANC CCI	Consider 1 dose level reduction. If already taking G-CSF, reduce 1 dose level.	Hold until ANC CCI	Reduce 1 dose level	Hold until ANC CCI	No reduction Recommend G-CSF in subsequent cycle
Grade 4 >7 days duration or >14-day cycle delay		Reduce 1 dose level Recommend G-CSF in subsequent cycle		Recommend G-CSF in subsequent cycle		Reduce 1 dose level Recommend G-CSF in subsequent cycle
Grade 4 Recurrent ^a						Reduce 1 dose level Recommend G-CSF in subsequent cycle
Dose Modification for Febrile Neutropenia						
Note: For hematologic toxicities, dose holds, and reductions - apply simultaneously to all drugs as indicated						
Grade 3 Initial incident	Hold until resolution	Consider 1 dose level reduction Recommend G-CSF in subsequent cycle	Hold until resolution	Consider 1 dose level reduction Recommend G-CSF in subsequent cycle	No change	
Grade 3 Recurrent ^a				Reduce 1 dose level Recommend G-CSF in subsequent cycle		
Grade 4				Reduce 1 dose level Recommend G-CSF in subsequent cycle		Reduce 1 dose level if not previously on G-CSF Reduce 2 dose levels if G-CSF was used Recommend G-CSF in subsequent cycle

Abbreviations: ANC = absolute neutrophil count; G-CSF = granulocyte-colony stimulating factor.

Grade 3: ANC < 1000/mm³; **Grade 4:** ANC < 500/mm³.

^a Recurrent toxicity refers to the same event occurring within the next 8 weeks (as measured from the stop date of the preceding event).

Dose Modification for Thrombocytopenia						
Note: For hematologic toxicities, dose holds, and reductions - apply simultaneously to all drugs as indicated						
	Abemaciclib		Irinotecan		Temozolomide	
Severity and Duration	Dose Hold	Dose Reduction	Dose Hold	Dose Reduction	Dose Hold	Dose Reduction
Grade 2 that causes >7-day cycle delay	Hold until platelets ≥ CCI	No change	No change		Hold until platelets ≥ CCI	No change
Grade 3 that causes >7-day cycle delay						Reduce 1 dose level
Grade 4 Initial incident		Consider 1 dose level reduction	Hold until platelets ≥ CCI	No change		Reduce 1 dose level
Grade 4 >7 days duration or >14-day cycle delay		Reduce 1 dose level		Reduce 1 dose level		If platelet count ever drops below 10,000/mm³, discontinue
Grade 4 Recurrent						

Grade 2: platelets < 75,000/mm³; **Grade 3:** platelets < 50,000/mm³; **Grade 4:** platelets < 25,000/mm³.

